#### 2.4.6.1.2 *Adverse events of special interest*

**Protocol-defined IAR:** The following summaries will be produced by primary SOC and PT, and by treatment group for PAP:

- Protocol-defined IARs
- Protocol-defined IARs by the worst severity
- Protocol-defined IARs started during infusion
- Protocol-defined IARs started between 0 hours (exclusive) and 3 hours (exclusive) post end of infusion
- Protocol-defined IARs started between 3 hours (inclusive) and 24 hours (inclusive) post end of infusion
- Protocol-defined IARs started between 24 hours (exclusive) and 72 hours (inclusive) post end of infusion
- Protocol-defined IARs started after 72 hours post end of infusion

In case there are IARs identified by the sponsor (before database lock) that the investigator did not agree to be an IAR, sponsor-identified IARs may be added to the list of investigator-identified IARs to define the protocol-defined IARs, and additional summaries may be produced.

A subset of protocol-defined IARs will also be defined programmatically by searching for preferred terms within Hypersensitivity reaction SMQs (identified using SMQ code 20000214 Broad and Narrow scope). The summaries of Hypersensitivity IARs will be provided by primary SOC and PT.

**Algorithm-defined IAR:** Summary of algorithm-defined IARs by primary SOC and PT will be provided for PAP.

#### 2.4.6.1.3 *Adverse events of other interest*

**Infections:** Infection AEs are already part of system organ class of Infections and Infestations in all TEAE displays. No separate display is planned.

**Bleeding:** Bleeding related TEAEs will be summarized using the standard MedDRA queries (SMQs) Hemorrhages (identified using SMQ code 20000038 broad and narrow scope).

#### 2.4.6.1.4 *Serious adverse events*

The following summaries will be provided by primary SOC and PT for PAP:

- Treatment-emergent serious adverse events

#### **2.4.6.1.5 Adverse events leading to permanent treatment discontinuation**

In this study, if the treatment is discontinued permanently, the patient is withdrawn from the study. A temporary dose interruption is not considered permanent discontinuation of study treatment. Any AEs leading to permanent treatment discontinuation will be summarized by primary SOC and PT - for PAP, ETP and cumulative over PAP and ETP. The listing of such AEs will include the olipudase alfa dose of the infusion prior to or during the occurrence of the AE leading to treatment discontinuation. Any AE leading to discontinuation of study treatment post-rescue in PAP will be provided in data listing.

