During the PAP, one rechallenge each will be allowed for doses administered at Week 0 (0.1 mg/kg olipudase alfa or placebo) and at Week 4 (0.3 mg/kg olipudase alfa or placebo). Patients who are unable to tolerate the rechallenge at those doses will be discontinued from the study. If a patient is discontinued due to inability to tolerate rechallenge (ie, a second dose of 0.3 mg/kg olipudase alfa), then an additional patient may be randomized. Any patient who successfully dose-escalates through Week 4, but cannot tolerate study drug infusions at later weeks, will continue in the trial at the Week 4 dose (ie, 0.3 mg/kg olipudase alfa or placebo) until end of study; likewise, any patient unable to tolerate a dose administered during later weeks will receive the HTD even if that dose is less than the target randomized dose and will continue in the ETP at this dose. The minimum active dose administered will be 0.3 mg/kg olipudase alfa.

During the ETP, the same dose-escalation conditions will apply for patients who cross over from the placebo arm during the PAP to the active treatment arm, except that patients unable to tolerate the rechallenge allowed each at Week 54 (0.1 mg/kg olipudase alfa) and at Week 58 (0.3 mg/kg olipudase alfa) will discontinue from the study and will not be replaced.

During the PAP and ETP, in-patient hospitalization will be required preinfusion and for at least 24 hours after the infusion during dose escalation (ie, through Week 16 and Week 70, respectively) and may be required at the quarterly and yearly visits up through the end of Year 2; in-patient hospitalization may be necessary during quarterly and yearly study visits in Years 3 through 5. For all other infusions, patients will be monitored for safety in the clinic for at least 1 hour. All patients will have an end of study/early discontinuation visit within 2 weeks after the last infusion of study treatment. In addition, all patients will receive a follow-up phone call for safety approximately 30 to 37 days after the last infusion of study drug.

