10.2 DEFINITION OF SOURCE DATA

Source data are all information, original records of clinical findings, observations, or other activities in a clinical trial necessary for the reconstruction and evaluation of the study. Source data are contained in source documents. Examples of these original documents and data records include hospital records, clinical and office charts, laboratory notes, memoranda, patients' diaries or evaluation checklists, pharmacy dispensing records, recorded data from automated instruments, copies or transcriptions certified after verification as being accurate and complete, microfiches, photographic negatives, microfilm or magnetic media, X-rays, patient files, and records kept at the pharmacy, the laboratories, and other departments involved in the clinical study.

All protocol-required information collected during the study must be recorded by the investigator or other study personnel in the source documentation for the study. The source documentation will be used to enter the protocol-required information into the eCRF. No data should therefore be directly entered into the eCRF.

10.3 HANDLING OF PATIENT TEMPORARY OR PERMANENT TREATMENT DISCONTINUATION AND OF PATIENT STUDY DISCONTINUATION

Study drug will be continued whenever possible; however, if study drug is stopped, it will be determined if the stop can be made temporarily as permanent discontinuation will be a last resort. Any discontinuation will be fully documented in the source and eCRF. In any case, the patient should remain in the study as long as possible.

Pregnancy

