10.3.4 Handling of patients after permanent treatment discontinuation

Any patient who discontinues participating in the study will be contacted by the study investigator to obtain information about the reason(s) for discontinuation and collection of any potential AEs.

If possible, all tests and evaluations listed for the end of study/early discontinuation visit in [Section 1.2](#) are to be carried out within 2 weeks of the last study drug infusion. If a patient fails to return for the necessary visits, then every effort must be made to contact the patient, determine the reason(s) for discontinuation, and record the reason(s) on the e-CRF.

In all cases, the sponsor must be notified of all study terminations as soon as possible and the reason for and date of withdrawal from the study must be recorded in the e-CRF and in the patient's medical record.

In addition, since the primary study comparison is based on intent to treat principle using all randomized patients with any study treatment, missing data, especially the key study assessments during the PAP (12 months) may potentially lead to biased results and challenges in assessing the treatment effect of the study drug. Therefore, all efforts should be made to continue to follow the patients for primary and key secondary endpoints, after the temporary or permanent discontinuation of treatment, in addition to the standard post study safety follow up. If possible, at the minimum, patients should be assessed at their regularly scheduled Week 52 visit (or as close as possible to Week 52) if treatment discontinuation occurred prior to that visit.

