10.4.2 General guidelines for reporting adverse events

See [Table 3](#) for an overview of AE reporting instructions.

- All AEs, regardless of seriousness or relationship to study treatment spanning from the signature of the informed consent form until the end of the study will be recorded on the corresponding eCRF.
- Except for IARs, whenever possible, diagnosis or single syndrome will be reported instead of symptoms. For IARs, all symptoms must be recorded separately.
- The investigator will specify the date of onset, intensity, action taken with respect to study drug, corrective treatment/therapy given, additional investigations performed, outcome, and opinion as to whether a reasonable possibility exists that the AE was caused by the study drug.
- The investigator should take appropriate measures to follow all AEs until clinical recovery has completed and laboratory results have returned to normal, or until progression has been stabilized, or until death, to ensure the safety of the patients.
- When treatment is prematurely discontinued, the patient's observations will continue until the end of the study as defined by the protocol.
- Laboratory, vital signs, or ECG abnormalities are to be recorded as AEs only if:
 - Symptomatic and/or
 - Requiring either corrective treatment or consultation, and/or
 - Leading to study drug discontinuation or modification of dosing, and/or
 - Fulfilling a seriousness criterion, and/or
 - Defined as an AESI (see [Section 10.4.1.3](#))

Table 3 - Summary of adverse event reporting instructions

Event category	Reporting timeframe	Specific events in this category	Case report form completion		
			AE form	Safety complementary form	Other specific forms
Adverse Event (non-SAE, non-AESI)	Routine	Any AE that is not SAE or AESI	Yes	No	No
Serious Adverse Event (non-AESI or AESI)	Expedited (within 24 hours)	Any AE meeting seriousness criterion per Section 10.4.1.2	Yes	Yes	No
Adverse Event of Special Interest	Expedited (within 24 hours)	Symptomatic overdose	Yes	Yes	No
		Pregnancy	Yes	Yes	Yes
		Infusion associated reactions (IAR)/Hypersensitivity reactions	Yes	Yes	No
		Laboratory values per Section 10.4.1.3 and Section 10.4.4.1	Yes	Yes	No

Abbreviations: AE = adverse event; AESI = adverse event of special interest; SAE = serious adverse event; ULN = upper limit of normal

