11.5.2.1 Primary efficacy analysis

The 2 primary efficacy endpoints (percentage change in spleen volume in MN from baseline to Week 52 [combined with change in SRS from baseline to Week 52 in the US only, and is referred to as the “combination spleen endpoint”]) and percentage change in DL_{CO} in percent predicted from baseline to 52 weeks) will be analyzed in the mITT population using the mixed model for repeated measures.

For percent change in DL_{CO} (% predicted) from baseline, the mixed model for repeated measures (MMRM) will include baseline DL_{CO} (% predicted), baseline age, treatment arm, study visit (Week 26, Week 52), and study visit by treatment arm interaction as covariates; have an unstructured variance-covariance matrix; and be fit using restricted maximum likelihood estimation. Comparisons between treatment arms will be made using least-square mean contrasts at the 52 week visit.

The analysis will include all DL_{CO} observations after baseline in the first 12 months of the study regardless of the treatment discontinuation status, with the exception that measurements made after the switch of treatment (eg, placebo patients switch to olipudase alfa after meeting the rescue criteria) will not be considered. For the primary analysis, missing data will not be imputed and will be assumed as Missing at Random (MAR).

Similar analyses will be performed for the spleen volume (MN) and the splenomegaly-related symptom score (SRS), when baseline value of the spleen volume (or SRS) will be used as covariate.

Descriptive assessment of MAR assumption and sensitivity analyses to assess the impact of missing data are described in the SAP.

Hypothesis tests will be 2-sided and adjusted for multiple comparisons to maintain a family-wise Type 1 error rate of 5%. The details of multiplicity adjustments are provided in [Section 11.5.4](#).

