The MMRM assumes data missing-at-random (MAR) and will include all DLco observations except for measurements made after the initiation of rescue therapy. In addition, for patients who do not have Week 52 value available but have a PFT value measured after Week 38 infusion (eg, patients discontinuing the study or initiating rescue therapy after Week 38 but before Week 52 may have the PFT measurements available from early discontinuation visit or right before rescue therapy starts), these values will be used as Week 52 value for analysis purposes; Week 52 DLco will not be considered missing in such situations. This idea is based on the clinical concept that PFT measurements are similar within a 12-week period.

The percentage change in spleen volume (MN) and the change in the splenomegaly-related score (for US, SRS is part of primary endpoints) will be analyzed using an analogous MMRM model.

The summary plots of the LS means from the MMRM of the percentage change in DLco (% predicted), the percentage change in spleen volume (MN) and the change in the splenomegaly-related score from baseline up to Week 52 with 95% CIs will be provided.

Sensitivity analyses for the primary efficacy endpoints to support robustness of results will include the following:

1. The MMRM described above will be run using the per-protocol population. This analysis will demonstrate whether the results vary depending on the population analyzed.
2. The MMRM described above will exclude observations made after the initiation of rescue therapy. As a sensitivity analysis, the observations collected after the initiation of rescue therapy will be included in the MMRM; the treatment arm for rescued patients will remain

as randomized treatment.

The MMRM planned for the primary efficacy analysis assumes MAR. To assess the robustness of the primary results to that assumption a pattern mixture model will be used (see [Section 2.6.6](#) for details).

3. The MMRM planned for the primary efficacy analysis assumes multivariate normality. To assess the robustness of conclusions under this assumption, nonparametric testing method will be used: A Wilcoxon-Mann-Whitney (WMW) will be used to compare the primary efficacy endpoints; missing Week 52 data will be imputed using LOCF, excluding patients who initiate rescue therapy.

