### *Imputation of missing data during the on-treatment period*

Missing DLco values during the on-treatment period will be imputed from other on-treatment measurements assuming MAR, using SAS® PROC MI.

Only DLco values collected during the on-treatment period will be included in the imputation model. This way, missing DLco values during the on-treatment period will be imputed based solely on observed on-treatment calculated DLco values.

The imputation model will include baseline DLco, baseline age and all observed DLco values at weeks 26 and 52 and will be stratified by treatment group of placebo and olipudase alfa. Since the

pattern of missing data could be non-monotone, a MCMC method will be used. A minimum value of 0 will be specified in order to avoid negative imputed DLco values.

Sample SAS code is provided below:

```
proc mi data=DATAIN out=DATAOUT nimpute=100 minimum=0;  
  var DLCO_BASE AGE_BASE DLCO_W26 DLCO_W52;  
  by TRTPN;  
run;
```

For the splenomegaly-related score endpoint which is collected at Weeks 14, 26, 38 and 52, the above code will be modified accordingly.

As stated above, the input dataset DATAIN will include only DLco values collected during the on-treatment period. Any DLco values collected after the treatment discontinuation (after last infusion +13 days) will be excluded from the input dataset. In practice, the MI procedure will generate imputed values for all missing values (whether on-treatment or post-treatment), but only imputed values during the on-treatment period will be kept in the final datasets that will be analyzed using ANCOVA. Imputed values during the post-treatment period will be discarded and replaced by imputed values described in the next section.

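### The SAP and the rechallenge rule withdraw patients who stop treatment from the study, while Protocol 10.3 and 10.3.4 ask that they be followed, if possible to Week 52 (minor)

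*SAP*

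**What the plan says.** **Text that ends participation**

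- SAP 2.4.6.1.5, without exception: "In this study, if the treatment is discontinued permanently, the patient is withdrawn from the study".
- Protocol 6.1, on the single rechallenge allowed at the Week 0 dose (0.1 mg/kg or placebo) and the Week 4 dose (0.3 mg/kg or placebo): "Patients who are unable to tolerate the rechallenge at those doses will be discontinued from the study". The clinical trial summary and 8.1.1 carry the same sentence. An additional patient may then be randomized. Patients who fail only at later doses stay in the trial on their highest tolerated dose.

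**Text that keeps patients in follow-up**

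- Protocol 10.3: "In any case, the patient should remain in the study as long as possible".
- Protocol 10.3.4: "all efforts should be made to continue to follow the patients for primary and key secondary endpoints, after the temporary or permanent discontinuation of treatment". The stated minimum, if possible, is the Week 52 assessment.
- Protocol 10.4.2, in the adverse event guidance, says that after premature treatment discontinuation the patient's "observations will continue until the end of the study as defined by the protocol".

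**Analysis rules that allow for off-treatment data**

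- Protocol 11.5.2.1 uses DLco observations "in the first 12 months of the study regardless of the treatment discontinuation status", apart from those made after a switch of treatment.
- SAP 2.4.5.1: the mixed model for repeated measures (MMRM) "will include all DLco observations except for measurements made after the initiation of rescue therapy".
- SAP 2.6.6, on the pattern-mixture imputation: "Any DLco values collected after the treatment discontinuation (after last infusion +13 days) will be excluded from the input dataset". That sentence has a purpose only if such values can be collected.

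**The concern.** Two rules cover the same patient. A site that follows the rechallenge sentence ends participation, while a site that follows 10.3.4 brings the patient back at Week 52.

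The choice decides whether primary endpoint data exist. A failed-rechallenge patient has been infused and so belongs to the modified intent-to-treat population (SAP 2.3.1.1). The discontinuation visit listed for this patient in Protocol 10.1 has no MRI and no pulmonary function test, and the first scheduled post-baseline ones are at Week 26. If participation ends, the patient has no post-baseline spleen volume or DLco value and adds nothing to either primary MMRM. The missing-at-random assumption then stands in for the data. If such patients would have lost their benefit, the estimated effect is too large for a comparison that 10.3.4 describes as based on the intent-to-treat principle.

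**Working it through.** **1. Is this a version difference or a declared departure?** No. The amendment history places the follow-up text of 10.3.4 and 11.5.2.1 in Amended Protocol 09 (18 September 2018). The SAP is based on Amended Protocol 11 (August 2019). SAP 1.5 lists its departures from the protocol, and this is not among them.

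**2. What does each passage actually require?**

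- Only 10.3.4 asks for endpoint follow-up to Week 52. It makes no exception for failed rechallenge.
- 10.3 points the same way in general terms.
- 10.4.2 is adverse event guidance and orders no MRI or pulmonary function test.
- 11.5.2.1 and SAP 2.4.5.1 say which data are used. They order no visit.
- The SAP sentence sits in a section on adverse event tables and drives no efficacy analysis. The SAP's own overview of treatment-emergent events (2.4.6.1.1) counts treatment discontinuation and study withdrawal separately.

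The conflict therefore concerns whether data are collected, not how collected data are analysed.

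**3. The plan's own figure.** Inputs from SAP 1.3: 36 patients randomized 1:1, 11% without a Week 52 result, DLco difference 25 and SD 20, two-sided 5%. 36 × 0.89 ≈ 32, or 16 per arm. Noncentral t power is 0.928, against 93% stated. The figure reproduces.

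**4. Illustrative bias.** The documents give no stopping rate, so the following is assumed: k of 18 olipudase alfa patients are lost this way, none on placebo, and each would have kept a share r of the benefit d.

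- Difference if all are followed = d × (18 − k + k·r) / 18.
- Relative overstatement when they are treated as missing at random = 18 / (18 − k + k·r) − 1.

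| k | r | Overstatement | DLco, planned 25 | Spleen volume, planned 30 |
|---|---|---|---|---|
| 0 | any | 0% | 25 | 30 |
| 1 | 0 | 18/17 − 1 = 5.9% | 23.6 | 28.3 |
| 2 | 0 | 18/16 − 1 = 12.5% | 22.2 | 26.7 |
| 1 | 0.5 | 18/17.5 − 1 = 2.9% | 24.3 | 29.2 |
| 2 | 0.5 | 18/17 − 1 = 5.9% | 23.6 | 28.3 |

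If each lost patient is replaced, so that 18 active patients are measured out of 18 + k randomized, the overstatement with r = 0 is (18 + k)/18 − 1 = k/18. That is 5.6% for k = 1 and 11.1% for k = 2.

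The case k = 2 is high. The planned allowance for missing results from all causes is 0.11 × 18 = 1.98 per arm, so this one cause would use all of it.

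**5. Would a primary result be at risk?** Take all 18 per arm as followed, r = 0, active-arm variance = SD² + p(1 − p)d² with p = k/18, two-sided 5%.

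- DLco power is 0.954 (k = 0), 0.921 (k = 1) and 0.877 (k = 2).
- Spleen volume power (d = 30, SD 11.8) stays above 0.99 throughout.

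**6. What already probes the bias?** The pattern-mixture analysis in SAP 2.6.6 imputes a return to baseline after treatment discontinuation for DLco, spleen volume and the splenomegaly-related score. Liver volume comes from the same MRI and is first in the secondary hierarchy. SAP 2.4.5.2 plans no sensitivity analysis for it and leaves one optional.

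**The case against.** The strongest reply is that nothing is left to protect. The reviewed protocol is Amendment 15 of November 2022, and its amendment history puts the data cutoff at the end of the PAP at 17 October 2019. Rewording cannot recover any Week 26 or Week 52 visit from that period. **This stands.** The value now lies in a correct statement of the rule and in transparent reporting of what was done.

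The second reply is that the group is tiny and the bias is already tested. In the Phase 1b study (Protocol section 4), all 5 patients remained at 3.0 mg/kg and no serious or severe events were reported. **This largely stands,** though 5 patients say little about rarity and liver volume is outside the planned test.

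The third reply is that failed rechallenge is a deliberate exception. The sentence can be read that way, but 10.3.4 carves none out, and SAP 2.4.6.1.5 covers every permanent discontinuation.

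Two stronger readings should be resisted:

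- A reader might infer that the SAP drops data from patients who stopped treatment. It does not: its primary MMRM keeps all DLco observations except those after rescue.
- A reader might infer that Protocol 10.1 forbids later MRI and lung function tests. Its short lists apply to the discontinuation visit only.

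**Conclusion.** The conflict holds and is undeclared. SAP 2.4.6.1.5 is wrong as written, and the rechallenge sentence in the summary, 6.1 and 8.1.1 contradicts 10.3 and 10.3.4. Severity is minor.

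In practice the effect is confined to patients who fail a second 0.1 or 0.3 mg/kg dose. The bias is 0 if none occur on olipudase alfa. The figures of about 6% to 12.5% (5.6% to 11.1% with replacement) rest on three assumptions that the documents do not supply: 1 or 2 losses in the active arm, none on placebo, and full return to baseline. Half-retained benefit without replacement gives 2.9% to 5.9%.

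It would be tempting to conclude that the primary result is biased or the study underpowered. The documents support neither: no stopping count is given, the planned power reproduces, and no primary conclusion is shown to change.

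**What to change.** 1. **SAP 2.4.6.1.5:** replace the sentence with the 10.3.4 rule. Permanent treatment discontinuation is not study withdrawal, and consenting patients are followed for primary and key secondary endpoints, if possible to Week 52.
2. **Protocol summary, 6.1 and 8.1.1:** say that patients who fail rechallenge in the PAP are discontinued from study treatment, and that the scheduled Week 26 and Week 52 MRI, pulmonary function tests and eDiary continue under 10.3.4 for those who agree. The visit lists in 10.1 need no change.
3. **Clinical study report:** state by arm how many patients who stopped treatment in the PAP were followed to Week 52 and how many were withdrawn.

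The cost is one SAP sentence, one protocol sentence in three places, and one short disposition count. No new procedure or analysis is needed.
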